9.8 Preparation and administration of patiromer oral suspension

The required number of patiromer sachets should be added to 40ml (3 tablespoons) of water in a glass and then stirred. A further 40ml (3 tablespoons) of additional water should be added and the suspension stirred thoroughly. The powder does not dissolve but instead forms a suspension. More water can be added to the mixture as needed for the desired consistency. The suspension should be taken as soon as prepared but it must be taken within 1 hour. If powder remains in the glass after drinking, more water should be added, the suspension stirred and the remaining solution drunk immediately. This should be repeated as needed to ensure the entire dose is administered.

If required apple juice may be used instead of water to prepare the mixture. Whilst patiromer can be mixed with cranberry juice, its use should be avoided where possible in this trial due to the potential of interactions with other medicinal products. Other liquids should be avoided as they may contain high amounts of potassium. The patiromer suspension may be taken with or without food. The powder should not be heated (e.g. microwaved), added to heated foods or liquids, or taken as a dry powder. Further information is provided in the current Summary of Product Characteristics and package insert.

Patiromer doses must not be split and should be taken as a single oral dose once daily. Patiromer should be taken preferably at the same time each day and should be taken at least 3 hours before or after other oral medicines. This recommendation is based on concerns about possible binding of patiromer to other medicines that might reduce their absorption. This has been tested in the medicines described below.

Medicines where there is reduced bioavailability/potential interaction when co-administered with patiromer

Administration of the following oral medicines with patiromer must be separated by at least 3 hours to prevent interaction

- ciprofloxacin
- levothyroxine
- metformin
- quinidine

Medicines where there is considered to be no clinically significant effect on bioavailability/potential interaction when co-administered with patiromer

At the discretion of the Investigator, the following oral medicines may be co-administered/administered within 3 hours prior to or after taking patiromer:

- · spironolactone, furosemide, digoxin,
- lisinopril, valsartan,
- · aspirin, clopidogrel,
- atorvastatin
- allopurinol, phenytoin
- amoxicillin, cephalexin, trimethoprim* (* increased risk of hyperkalaemia)
- apixaban, rivaroxaban, and warfarin.

This list may be extended as further research becomes available.

Note that at the current time there is no information available on co-administration with eplerenone therefore administration should be separated from patiromer by at least 3 hours.

Missed and omitted patiromer doses

Participants should not discontinue treatment without consulting the research team.

If a dose of patiromer is missed, it should be taken as soon as possible on the same day unless it is almost time to take the next dose in which case you should not take the forgotten dose. A double dose

Version 5.0 22 July 2021 Page 48 of 82

should not be taken on the following day to make up for a missed dose. Participants should just resume taking their next normal dose at their usual time. If doses of patiromer are missed on more than two consecutive days, participants **must** contact the research team for advice. Participants must not discontinue patiromer without consulting the trial team. Increases in serum potassium may occur within 2-4 days after the last dose of patiromer.

If the participant stops patiromer for any reason, they must also stop their MRA and contact the investigator.

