8.9 Withdrawal criteria

Participants may choose to withdraw at any time, either from the intervention (patiromer or MRA), the follow-up procedures or from follow-up through their electronic medical record. Reasons for withdrawal will be recorded, providing the participant agrees. Participants who withdraw from the intervention or

Version 5.0 22 July 2021 Page 42 of 82

follow-up procedures should cease to take IMP and revert to standard-care. The costs of patiromer or MRA would no longer be reimbursed from the trial budget.

Participants who choose to stop patiromer-IMP only should have the dose of MRA adjusted to prevent hyperkalaemia. Participants who choose to stop MRA-IMP only should have the dose of patiromer adjusted to prevent hypokalaemia. Further guidance is provided in Appendix 3. Changes in serum potassium and clinical status should be evaluated carefully after any dose adjustments.

Participants may be withdrawn from IMP by their investigators if deemed appropriate (e.g. the investigator is concerned about a participant's safety because of uncertainty about adherence to IMP). Safety will be assessed by research nurses and/or investigators at each visit and after the occurrence of each SAE/SAR. Participants who have had an SAR (e.g. a hospital admission for the management of hyper- or hypo-kalaemia) should be reassessed for their ability to understand and comply with IMP dosing instructions.

- If the participant is, in the investigator's opinion, no longer able or willing to comply with treatment instructions, then they should stop one or both IMP and revert to standard-care, even if they have not experienced an SAE or SAR.
- Participants who are assigned to patiromer and who have or develop hyperkalaemia (serum potassium >5.0mmol/L), even if they have been withdrawn from spironolactone or eplerenone IMP, may continue on or restart patiromer.

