9.9 Administration of spironolactone and eplerenone

Spironolactone tablets must be administered orally and tablets should be swallowed whole with water and preferably taken with a meal. Eplerenone tablets must be administered orally and should be swallowed whole with water but may be taken with or without food. Use of unlicensed oral suspensions or solutions is not permitted.

Missed and omitted spironolactone or eplerenone doses

Participants should not discontinue treatment without consulting the research team.

Participants should take a missed dose as soon as possible on the same day unless it is almost time to take the next dose in which case the forgotten dose should be omitted. A double dose should not be taken on the following day to make up for a missed dose. Participants should just resume taking their next normal dose at their usual time. If doses of spironolactone or eplerenone are missed on three or more consecutive days, participants **must** be advised to contact the research team for advice.

If the participant stops their MRA for any reason, then they should also stop their patiromer and contact the investigator.

If the participant develops persistent vomiting and/or diarrhoea lasting more than two hours or if they become acutely unwell for any other reason they should stop MRA (control group) or both MRA and patiromer (intervention group) until they have recovered or, if symptoms are severe or persistent, seek medical advice either from their general practitioner or emergency services. The investigator should be contacted as soon as possible to determine the need for assessments of serum potassium and adjustment of MRA or patiromer dose.

Dosage modifications

The dose of patiromer and MRA should be altered according to the serum potassium concentration according to the schedule shown in section 8.6.

Trial supplies of patiromer-IMP must not be used for the emergency treatment of hyperkalaemia in either group and must not be used to manage hyperkalaemia in patients assigned to standard care.

The dose of MRA may also be limited by blood pressure and renal dysfunction. The dose of MRA should be reduced or stopped if the patient has symptomatic hypotension or eGFR falls persistently to <30mL/min/1.73m² after other therapeutic actions to improve hypotension and renal dysfunction have been undertaken, if appropriate (see below).

For eplerenone only:

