Appendix 3: Managing Discontinuation of Patiromer or MRA

[figure not shown]
Patients who stop patiromer should have the dose of MRA adjusted to prevent hyperkalaemia. If serum potassium is in the normal range, the dose of MRA should be halved or reduced to 25mg/day, whichever is higher. Serum potassium should be re-checked in 7-12 days.

Patients who stop their MRA should have the dose of patiromer adjusted to prevent hypokalaemia. Many patients will be on other potassium retaining treatments and may still benefit from patiromer. If serum potassium is in the normal range, stop patiromer and re-check serum potassium in 7-12 days. If serum potassium exceeds 5.0mmol/L, patiromer should be re-started.

Version 5.0 22 July 2021 Page 70 of 82

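### Protocol 9.8 has a participant who stops patiromer stop the MRA too, while 8.9 and Appendix 3 keep the MRA at an adjusted dose; the reverse direction conflicts in part

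*Protocol*

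**What the plan says.** **When patiromer is stopped.** Section 9.8, under missed and omitted doses, states: "If the participant stops patiromer for any reason, they must also stop their MRA and contact the investigator". Section 8.9 says: "Participants who choose to stop patiromer-IMP only should have the dose of MRA adjusted to prevent hyperkalaemia". It refers the reader to Appendix 3, which says "Patients who stop patiromer should have the dose of MRA adjusted to prevent hyperkalaemia" and continues: "If serum potassium is in the normal range, the dose of MRA should be halved or reduced to 25mg/day, whichever is higher". Section 8.3 covers a participant who loses capacity: patiromer stops and the MRA dose is adjusted in line with standard care. Section 9.13 covers poor compliance in participants on both drugs: investigators are to consider withdrawing patiromer and managing the participant on MRA alone.

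**When the MRA is stopped.** Section 9.9 says: "If the participant stops their MRA for any reason, then they should also stop their patiromer and contact the investigator". Section 8.9 says: "Participants who choose to stop MRA-IMP only should have the dose of patiromer adjusted to prevent hypokalaemia". Appendix 3 says "Patients who stop their MRA should have the dose of patiromer adjusted to prevent hypokalaemia" and then: "If serum potassium is in the normal range, stop patiromer and re-check serum potassium in 7-12 days". It restarts patiromer if potassium goes above 5.0 mmol/L. Sections 8.9 and 9.13 also let a patiromer-arm participant with hyperkalaemia stay on, or go back to, patiromer after withdrawal from the MRA.

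**The concern.** Section 3 identifies discontinuing one agent but not the other as an important risk. It relies on the protocol, labelling, a safety card and education to control it. Section 1 explains why: MRA without patiromer risks hyperkalaemia, and patiromer without MRA risks hypokalaemia. Section 9.8 adds that potassium may rise within 2-4 days of the last patiromer dose. Instructions for this event therefore need to be unambiguous, yet a participant or site who looks in one section finds a different instruction from one who looks in another.

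There is also a data aspect. MRA dose is a secondary endpoint (Section 4.7) and one of the criteria in the interim analysis (Section 11.5). Under intention to treat, a participant who stopped patiromer would count at whatever MRA dose the section followed had produced. A site that obeys one section also departs from another, which leaves the classification of protocol deviations unclear.

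**Working it through.** The check is a comparison of text; there is no figure in the plan to reproduce.

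**Direction 1: patiromer stopped, what happens to the MRA?**

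| Place | Situation | MRA |
|---|---|---|
| 9.8 | participant stops, whatever the reason | stopped (mandatory wording) |
| 8.9 | participant chooses to stop patiromer only | dose adjusted |
| Appendix 3 | patiromer stopped, potassium normal | larger of half the dose and 25 mg/day |
| 8.3 | loss of capacity | dose adjusted |
| 9.13 | poor compliance on both drugs | continues alone, if patiromer is withdrawn |

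The 9.8 and 8.9 rows cover the same event, a stop initiated by the participant, so the conflict there is direct. The 8.3 and 9.13 rows concern withdrawal managed by the study or care team. They show that the protocol foresees MRA without patiromer, but they do not by themselves contradict an instruction addressed to participants.

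**Size of the gap in direction 1.** Inputs: the Appendix 3 rule, which applies at normal potassium, and the expected median spironolactone dose of about 100 mg/day in the patiromer arm (Section 2). For a current dose D of 25 mg/day or more, Appendix 3 gives max(D/2, 25) and 9.8 gives 0.

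| D (mg/day) | 9.8 | Appendix 3 |
|---|---|---|
| 200 | 0 | max(100, 25) = 100 |
| 100 | 0 | max(50, 25) = 50 |
| 50 | 0 | max(25, 25) = 25 |
| 25 | 0 | max(12.5, 25) = 25 |

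The two rules do not coincide at any of these doses. Because the Appendix 3 result is never below 25 mg/day, they cannot coincide at any D of 25 mg/day or more.

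**Direction 2: MRA stopped, what happens to patiromer?**

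| Place | Situation | Patiromer |
|---|---|---|
| 9.9 | participant stops, whatever the reason | stopped |
| 8.9 | participant chooses to stop MRA only | dose adjusted |
| Appendix 3 | MRA stopped, potassium normal | stopped; restarted above 5.0 mmol/L |
| 8.9 and 9.13 | hyperkalaemic, withdrawn from MRA | may continue or restart |

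At normal potassium, 9.9 and Appendix 3 agree. The remaining conflict is between the unconditional wording of 9.9 and two other provisions: the dose adjustment in 8.9, and the permission for hyperkalaemic participants to continue patiromer.

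**Does the text rank or order the rules?** Sections 9.8 and 9.9 do not call the stop temporary and do not point to 8.9 or Appendix 3. Section 9.9 refers the reader to Section 8.6 for dose modification, but 8.6 is the section on emergency unblinding.

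**The case against.** The best defence is that the rules are sequential and addressed to different people. The 9.8 and 9.9 sentences sit among instructions to participants, who are told not to discontinue without consulting the team. Section 8.9 and Appendix 3 describe dose adjustment, which is a prescriber's act. On that reading the participant stops both drugs and calls, and the investigator then sets the dose. The next paragraph of 9.9 uses this sequence for acute illness: stop until recovered, then contact the investigator, who considers potassium checks and dose adjustment.

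This reading is reasonable and may be what was intended, but the visible text does not state it. The acute-illness paragraph limits its stop in time; the disputed sentences do not. Section 8.9 also deals with stops that the participant chooses, so it cannot be set aside as a different event. The Appendix 3 figure is not shown and might set out an order of steps. The safety card and labels are not available either. The point is therefore limited to the text that can be read.

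Three further parts of the defence stand:
- A reader might infer that the contradiction is symmetrical. It is not: Appendix 3 supports 9.9 when potassium is normal.
- A reader might infer that every patiromer-arm discontinuation is affected. Section 9.8 speaks of a participant who stops; withdrawal managed by the team is dealt with in 8.3 and 9.13.
- A reader might infer that the dose and outcome comparisons are distorted. The SAP (1.6.1, 1.6.3 and 2.6) reports early closure with four randomised, no formal analyses, and listings only for randomised data. No such comparison will be made.

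**Conclusion.** The inconsistency is real. It is direct when a participant stops patiromer: one section requires the MRA to stop, and another section and an appendix keep it at an adjusted dose. It is partial when the MRA is stopped first.

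The contrast of 0 against 50 mg/day assumes normal potassium and the expected median of 100 mg/day. If the 9.8 stop was meant as interim, the gap would last only until the investigator acts.

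The importance lies in participant safety, on a risk the protocol itself singles out. The effect on the reported analysis is negligible with four participants randomised. What remains on the data side is the deviation listing in SAP 2.3, where compliance with one section could be recorded as departure from another. The documents do not show whether any of the four stopped one drug. Nothing here implies that either rule is clinically preferable.

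**What to change.** The sponsor should reconcile Sections 8.3, 8.9, 9.8, 9.9 and 9.13 and Appendix 3 so that a given event leads to one instruction.

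- If 9.8 and 9.9 are the participant's immediate action, and 8.9 and Appendix 3 the investigator's follow-on action, say so in each place.
- State whether 9.8 and 9.9 apply only to stops initiated by the participant, and how they relate to the hyperkalaemia provision in 8.9 and 9.13.
- Add cross-references between these sections, and correct the pointer in 9.9 to Section 8.6.
- Check that the safety card, labels and educational material carry the same instruction.
- In the SAP 2.3 deviation listing, state which section was used as the reference for any randomised participant who stopped one drug.

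The cost is protocol wording and a check of participant material, with no added visits, tests or data. Because the trial has closed, the protocol changes matter mainly for the record and for any later use of this protocol. The choice of rule belongs to the sponsor and its clinical advisers.

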9.9 Administration of spironolactone and eplerenone

Spironolactone tablets must be administered orally and tablets should be swallowed whole with water and preferably taken with a meal. Eplerenone tablets must be administered orally and should be swallowed whole with water but may be taken with or without food. Use of unlicensed oral suspensions or solutions is not permitted.

Missed and omitted spironolactone or eplerenone doses

Participants should not discontinue treatment without consulting the research team.

Participants should take a missed dose as soon as possible on the same day unless it is almost time to take the next dose in which case the forgotten dose should be omitted. A double dose should not be taken on the following day to make up for a missed dose. Participants should just resume taking their next normal dose at their usual time. If doses of spironolactone or eplerenone are missed on three or more consecutive days, participants **must** be advised to contact the research team for advice.

If the participant stops their MRA for any reason, then they should also stop their patiromer and contact the investigator.

If the participant develops persistent vomiting and/or diarrhoea lasting more than two hours or if they become acutely unwell for any other reason they should stop MRA (control group) or both MRA and patiromer (intervention group) until they have recovered or, if symptoms are severe or persistent, seek medical advice either from their general practitioner or emergency services. The investigator should be contacted as soon as possible to determine the need for assessments of serum potassium and adjustment of MRA or patiromer dose.

Dosage modifications

The dose of patiromer and MRA should be altered according to the serum potassium concentration according to the schedule shown in section 8.6.

Trial supplies of patiromer-IMP must not be used for the emergency treatment of hyperkalaemia in either group and must not be used to manage hyperkalaemia in patients assigned to standard care.

The dose of MRA may also be limited by blood pressure and renal dysfunction. The dose of MRA should be reduced or stopped if the patient has symptomatic hypotension or eGFR falls persistently to <30mL/min/1.73m² after other therapeutic actions to improve hypotension and renal dysfunction have been undertaken, if appropriate (see below).

For eplerenone only:

Co-administration with mild to moderate CYP3A4 inhibitors: Eplerenone dosing should not exceed 25 mg daily when mild to moderate inhibitors of CYP3A4 are co-administered with eplerenone (e.g. erythromycin, saquinavir, amiodarone, diltiazem, verapamil, or fluconazole).

Version 5.0 22 July 2021 Page 49 of 82

9.10 Known drug reactions and interaction with other therapies

Patiromer

Patiromer binds potassium in the gastrointestinal tract. It is insoluble and is not absorbed. Patiromer does however have the potential to bind with oral co-administered medicinal products, which could decrease their gastro-intestinal absorption. Therefore, as a precautionary measure, administration of patiromer should be separated by at least 3 hours from other oral medicines unless listed as permitted at investigator-discretion in Section 9.8.

Spironolactone and eplerenone

The concomitant use of medicines known to cause hyperkalaemia with spironolactone or eplerenone may result in severe hyperkalaemia and should be withdrawn unless the investigator believes this not in the patient's best interest. Management of hyperkalaemia that cannot be managed by adjusting doses of MRA (or patiromer if assigned to this group) will follow the Renal Association guidelines of 2020 (https://renal.org/sites/renal.org/files/RENAL%20ASSOCIATION%20HYPERKALAEMIA%20GUIDELINE%202020.pdf).

Controversy persists on possible adverse consequences of taking MRA in conjunction with the combination of both an angiotensin converting-enzyme (ACE) inhibitor and an angiotensin receptor blocker (ARB). Investigators should avoid such practice.

Strong inhibitors of CYP 3A4 (e.g. itraconazole, ketoconazole, clarithromycin, telithromycin and nefazodone) may interfere with MRA metabolism and should be avoided wherever possible in patients taking MRAs. Eplerenone dosing should not exceed 25 mg daily when mild to moderate inhibitors of CYP3A4 are co-administered with eplerenone (e.g. erythromycin, saquinavir, amiodarone, diltiazem, verapamil, or fluconazole).

Caution is required with co-administration of MRA with the following medicines:

- Heparin and low molecular weight heparins
- Non-steroidal anti-inflammatories (NSAIDs)
- Trimethoprim or trimethoprim containing combination products e.g. co-trimoxazole
- Alpha-1-blockers (e.g. prazosin, alfuzosine) and other antihypertensive medicines
- Tricyclic anti-depressants, neuroleptics, amifostine, baclofen
- Glucocorticoids, tetracosactide
- Cholestyramine
- Digoxin and warfarin: caution is warranted particularly when dosed near the upper limit of therapeutic range
- Potassium supplements and potassium sparing diuretics e.g. amiloride.

The current Summary of Product Characteristics should be consulted for detailed information on interactions with other medicinal products.

9.11 Concomitant medication

Permitted concomitant medicines

All patients should be receiving loop diuretics and most will already be taking an MRA.

We expect that most patients will also be receiving one (only one) of the following agents: ACE inhibitors, ARBs, sacubitril-valsartan. Many will also receive beta-blockers and anti-thrombotic agents. Some patients will also be receiving thiazide diuretics, digoxin and ivabradine. Many patients will be receiving non-cardiovascular medications for various indications.

Version 5.0 22 July 2021 Page 50 of 82

The patients enrolled in this trial are inherently unstable and therefore no attempt to stabilise medications prior to enrolment is considered feasible. Investigators should attempt to stabilise and optimise treatment after randomisation during follow-up according to guidelines (investigators may choose to follow NICE, SIGN or ESC guidelines).

Where the dose of MRA is limited by hypotension or renal dysfunction, the investigator should consider whether reducing the dose of loop diuretic is possible. Thiazide diuretics could also be withdrawn but that may lead to marked fluid retention and therefore care is required. If the patient is severely congested and it is not possible to reduce the dose of diuretics then:

- a) The dose of ACE inhibitor may be reduced to 2.5mg/day of Ramipril or enalapril 2.5mg bd or similar, since there is little evidence from randomised trials that outcomes are better on higher compared to lower doses of ACE inhibitors for patients with moderate or severe heart failure (14). This may also be true for ARB and sacubitril-valsartan.
- b) For patients in atrial fibrillation (about half of this population) there is little evidence that betablockers are effective and evidence that reducing ventricular rate below 75bpm may be deleterious (16). Accordingly, reducing the dose of beta-blockers is advised to allow resting heart rate to rise above 75bpm.

Prohibited concomitant medicines

The following medicines are prohibited for all participants for safety reasons:

- Combined use of both an ACE inhibitor and ARB
- Lithium
- Cyclosporin
- Tacrolimus

The following medicines are prohibited for participants treated with eplerenone (patients must be switched to spironolactone during co-administration of these agents)

- Strong inhibitors of CYP 3A4 e.g. itraconazole, ketoconazole, ritonavir, nelfinavir, clarithromycin, telithromycin and nefazodone.
- Strong CPY3A4 inducers (e.g. rifampicin, carbamazepine, phenytoin, phenobarbital, St John's Wort)

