 Participants may be reconsidered for the trial once such interventions are no longer considered necessary.
 - Patients with a serum potassium ≤5.0mmol/L should be initiated on spironolactone or have the
 dose increased up to 100mg/day and randomised only if serum potassium exceeds 5.0mmol/L.
 Those intolerant of or unwilling to take spironolactone should be offered eplerenone titrated to
 a maximum dose of 50mg/day.
 - A run-in period of up to 35 days is permitted (the run-in period will usually occur during hospitalisation or a course of day-care or intense management).
- 2. After ingestion of a test-dose of patiromer,
 - a) the patient is willing to continue in the trial
 - b) the investigator considers the patient can follow instructions on preparing patiromer

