7.2 Exclusion criteria

For the Screening Log & Registry

None

For the Randomised Trial

- 1. eGFR <30ml/minute/1.73m² (if clinically appropriate, the dose of other agents such as loop diuretics, ACE inhibitors, angiotensin receptor blockers, beta-blockers and sacubitril-valsartan may be adjusted to allow eGFR to increase)
- 2. Systolic BP <90mmHg
- 3. Uncorrected valve disease as the main cause of heart failure in the investigators opinion

Version 5.0 22 July 2021 Page 26 of 82

- 4. Hepatic encephalopathy or known severe liver disease
- 5. Infection currently requiring intravenous antibiotics or temperature >38oC
- 6. Myocardial ischaemia currently requiring intravenous therapy or coronary intervention in the previous 7 days
- 7. Arrhythmia requiring urgent cardioversion or intravenous therapy
- 8. Severe hyperkalaemia requiring, in the investigator's opinion, intravenous treatment or a potassium-binding agent
- 9. The patient is already receiving a potassium-binding agent (this includes patiromer) or the treating physician has already decided to use one
- 10. Known hypersensitivity to patiromer or any of the excipients
- 11. Known intolerance to both spironolactone and eplerenone (not including hyperkalaemia)
- 12. Known hypersensitivity to the active substance or excipients of spironolactone and eplerenone as per the current Summary of Product Characteristics (Note: actual medicine supplied to participants will vary depending on local arrangements)
- 13. Women of childbearing potential. For the purposes of this trial this means any woman aged <60 years unless they have had a hysterectomy or bilateral tubal ligation or are aged >50 years and have undergone the menopause and had amenorrhea for at least 3 years
- 14. Patients taking the following systemic medicines:
 - strong inhibitors of CYP 3A4 (e.g. itraconazole, ketoconazole, ritonavir, nelfinavir, clarithromycin, telithromycin and nefazodone)
 - Lithium
 - Tacrolimus or Cyclosporin
- 15. The combination of an angiotensin converting enzyme (ACE) inhibitor and an angiotensin receptor blocker (ARB)
- 16. Rare hereditary problems of galactose or fructose intolerance, Lapp lactase deficiency or glucosegalactose malabsorption
- 17. Known amyloid heart disease
- 18. Cancer likely to cause death or major disability within the next three years
- 19. Patients requiring mechanical circulatory support, and

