- Immediately after randomisation: Those assigned to standard care should have the dose of MRA reduced unless serum potassium is ≥6.0mmol/L, in which case MRA should be temporarily suspended altogether until serum potassium is <5.0mmol/L. Patients with a serum potassium >5.0mmol/L who are not taking any dose of MRA may need the dose of other agents that increase potassium reduced. Those assigned to patiromer should continue to receive the dose of MRA administered at the time of randomisation unless serum potassium is ≥6.0mmol/L, in which case MRA should be temporarily suspended and patiromer continued until serum potassium is <6.0mmol/L. If serum potassium is ≥6.0mmol/L, also seek medical advice and treat according to guidelines. If intravenous treatment or a potassium-binding agent for the treatment of severe hyperkalaemia is required in the investigators opinion, the participant can be randomised only after these treatments have been stopped.
- Maintenance Phase: doses should follow the scheme shown in the tables below.
- Participants who do not develop a serum potassium >5.0mmol/L despite 100mg/day of spironolactone or 50mg/day of eplerenone within 35 days are not eligible for the randomised trial and will return to standard care. The clinician responsible for care should select the most appropriate dose of MRA for the participant. Under these circumstances, this will usually be 50mg/day of spironolactone or eplerenone. Participants will continue to be followed in the registry and may be reconsidered for the trial at any time should they become eligible.

If eGFR falls below 30mls/min/1.73m²or systolic blood pressure below 90mmHg prior to randomisation, the participant is not eligible for randomisation until these exclusion criteria have resolved. Under these circumstances, clinicians responsible for care should decide whether to continue the MRA and at what dose. Those excluded will continue to be followed in the registry and may be reconsidered for the trial at any time should they become eligible.

The following maximum doses of MRA are permitted for participants in the intervention arm after randomisation:

• **Spironolactone:** 200mg once daily. All doses must be taken orally.

• **Eplerenone:** 50mg once daily. All doses must be taken orally.

only those intolerant of, or unwilling to take, spironolactone should be offered eplerenone.

Version 5.0 22 July 2021 Page 46 of 82

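### Section 9.11 requires eplerenone users given a strong CYP3A4 inhibitor or inducer to switch to spironolactone, with no exception for those who could not tolerate or had refused it

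*Protocol*

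**What the plan says.** Section 9.11 of the protocol has a list introduced by "The following medicines are prohibited for participants treated with eplerenone". A parenthesis then gives the fallback: "patients must be switched to spironolactone during co-administration of these agents". The list has two items. The first is strong CYP3A4 inhibitors. The second begins "Strong CPY3A4 inducers (e.g. rifampicin, carbamazepine, phenytoin, phenobarbital" and ends with St John's Wort.

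Other sections say who takes eplerenone. Section 7.1, on the run-in, says "Those intolerant of or unwilling to take spironolactone should be offered eplerenone". Section 9.7 makes this a restriction, "only those intolerant of, or unwilling to take, spironolactone should be offered eplerenone", and repeats it under the titration tables. Section 3 supplies eplerenone to participants who develop gynaecomastia or other feminising effects on spironolactone. The Trial Summary tells existing eplerenone users with no contraindication to spironolactone to change over at baseline or during run-in.

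The SAP does not deal with the point.

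**The concern.** The two sets of text do not fit well together. Eplerenone is the second-choice MRA, kept mainly for people for whom spironolactone has failed or been refused. The Trial Summary also moves most other eplerenone users to spironolactone early on. When one of those who remain needs a listed agent, section 9.11 gives a mandatory instruction to use spironolactone, with no condition and no second option.

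The stake is the treatment of individuals, not inference. An investigator working from section 9.11 is told to give a drug the participant could not tolerate or would not take. With a short antibiotic course in someone who changed drug because of gynaecomastia, this matters little. With a long-term enzyme inducer, the period of co-administration could be the rest of follow-up. An investigator who sensibly holds eplerenone instead is departing from the wording of section 9.11, and section 14.5 does not allow planned deviations.

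**Working it through.** The point is a treatment rule, so the check is mainly a comparison of the relevant text.

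1. **The rule.** The agents are prohibited first. The switch applies when one is given anyway. Because the parenthesis speaks of a period of co-administration, the plan expects this to happen sometimes. No exception, alternative or cross-reference is given.

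2. **Who is covered.** Sections 3, 7.1 and 9.7 and the Trial Summary together leave on eplerenone mainly those intolerant of spironolactone, unwilling to take it, or troubled by its feminising effects. For these people the fallback is the drug they left or declined.

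3. **Do the entry criteria remove them?** Mostly not. Exclusion 11 begins "Known intolerance to both spironolactone and eplerenone (not including hyperkalaemia" and so removes only people who can take neither drug. Exclusion 12 covers known hypersensitivity to spironolactone and eplerenone. Depending on how its conjunction is read, it may remove some people hypersensitive to spironolactone alone. It does not remove those with gynaecomastia, other intolerance or a refusal.

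4. **Can a listed agent arise?** Strong inhibitors exclude at entry (exclusion 14), so for them the gap concerns agents started later. Inducers are not named as a class in exclusion 14, section 9.10 or section 9.12, although section 9.10 refers to the SmPC and section 9.12 discourages herbal supplements. Section 9.8 lists phenytoin, one of the inducers named in section 9.11, among medicines that may be taken close to patiromer. The protocol therefore contemplates participants on phenytoin.

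5. **Does the switch end the interaction caution?** Not for strong inhibitors. Section 9.10 says they "should be avoided wherever possible in patients taking MRAs", which includes spironolactone.

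6. **Numbers.** The documents do not say how many would meet the rule. The only related figure is section 3's assumption that 10% of those on higher-dose spironolactone will change to eplerenone for gynaecomastia. Applied to the 999 planned for the patiromer arm, 0.10 × 999 = 99.9, about 100. That is consistent with the protocol's own bound of fewer than 200. It counts one route to eplerenone only.

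   As an illustration on two assumed ranges that are not in the documents, suppose 5–15% of 1,998 randomised participants use eplerenone because they cannot or will not take spironolactone, and 1–5% of those need a listed agent:
   - Low end: 0.05 × 1,998 = 99.9; 99.9 × 0.01 = 1.0 participant; 1/1,998 = 0.05%.
   - High end: 0.15 × 1,998 = 299.7; 299.7 × 0.05 = 15.0 participants; 15/1,998 = 0.75%.

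   SAP section 1.6.1 records that only 4 participants were randomised.

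**The case against.** The strongest reply is that the protocol already resolves the case elsewhere. Section 8.9 states that "Participants may be withdrawn from IMP by their investigators if deemed appropriate". Sections 8.9 and 9.13 go further: a participant who is no longer able or willing to follow treatment instructions should stop one or both trial drugs and return to usual care, even without an adverse event. Inability and unwillingness are the two conditions at issue here. Section 9.13 also requires withdrawal when continuing is judged unsafe, and section 8.9 lets a participant stop the MRA at any time. Exclusion 12 may keep out some hypersensitive patients. Section 9.11 sets no spironolactone dose, and the Trial Summary allows doses as low as 25 mg once a week. The purpose of the rule, keeping eplerenone apart from these agents, is sound.

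Much of this stands. A reader might infer that the protocol contradicts itself, or that it forces participants onto a drug they refused. The documents do not support either reading, because the general provisions give a way out and participants keep the right to stop.

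The reply does not remove the defect. Those provisions are general safety and adherence rules. They do not qualify the specific mandatory sentence, and that sentence does not point to them. What they offer is stopping trial medication. Although section 8.9 allows restarting, none of them tells the investigator to hold eplerenone for the period of the interacting drug. Freedom over dose helps where intolerance is dose-related, but not where the participant declines spironolactone altogether.

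**Conclusion.** The point holds as a small defect in a treatment rule. For most of the people it covers, section 9.11's unconditional switch is the wrong instruction. It is most relevant to long-term strong inducers, and narrower for strong inhibitors, which are screened out at entry. Severity is minor.

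It would be tempting to read section 3's 10%, or its bound of fewer than 200, as the number affected. That is not supported: those figures count gynaecomastia switches during the study, and are neither the whole eplerenone group nor its ceiling. The illustrative 1 to 15 participants rests entirely on assumed shares. In the trial as run, at most 4 randomised participants could have met the rule.

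Nor does the point reach the trial's results. Power, endpoints and analysis are unaffected. That the defect exists is clear from the text; its practical consequence is small.

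**What to change.** Reword the parenthesis in section 9.11 along these lines: use a non-interacting alternative where possible; if the listed agent is unavoidable, switch to spironolactone only if the participant tolerates and accepts it; otherwise withhold eplerenone during co-administration. The investigator then manages patiromer under Appendix 3 and rechecks potassium, creatinine and blood pressure at 7–12 days and again at 30–45 days.

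The new wording should say how section 9.9 and Appendix 3 fit together. Section 9.9, under which a participant who stops the MRA also stops patiromer, applies until the investigator has been contacted. Appendix 3 then governs the investigator's management.

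The cost is one reworded parenthesis and the cross-references. Both rechecks are already required after a dose change (sections 8.1.2 and 9.7). The downside is that a few participants on long-term inducers may lose MRA treatment for a prolonged period, and patiromer too if their potassium is normal. They remain in follow-up and in the intention-to-treat analysis, and section 8.9 allows trial medication to be restarted. With the trial closed, the change matters mainly if this treatment text is reused.
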